#### Time to hospital discharge survival

Time to hospital discharge is the time in the hospital after first study treatment in days (*date of discharge - first dose date + 1*). Patients who die before leaving the hospital will be considered failures (did not achieve hospital discharge), *date of death – first dose date +1* and censored. In the case that a patient is still hospitalized at time of analysis or withdraws from the study before leaving the hospital, they will be censored at their date of last assessment in the data cut or early discontinuation date, respectively.

The time to hospital discharge survival will be analyzed using Kaplan-Meier methods. If data allows, survival estimates will be stratified by baseline clinical status. The Cox models adjusting for baseline randomization strata may be performed.

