- b) If the month is unknown, then assign 'December'.
- c) If the day is unknown, then impute to the last day of the month.

Imputing partial death dates:

- a) If the month and/or year are unknown, the death date will not be imputed.
- b) If the day is missing, then assign '01'.
- c) If imputing the first day of the month results in a negative overall survival time, the patient will be censored for overall survival at the randomization date.

A patient data listing will be provided showing all patients with missing values for the primary endpoint. For these patients, the listing will provide all observed data relating to the primary endpoint (i.e. all measurements recorded prior to the missing value, any measurements recorded after the missing value, important baseline characteristics, the recorded reason for study discontinuation, and the date of study discontinuation). The listing will also provide the imputed date(s) used in the primary analysis.

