#### Time to Improvement

Time to improvement is the time in which the patient sees a decrease after first study treatment in the WHO 7-point ordinal scale from baseline to a value at least one level lower in days (*date of decrease in WHO scale - first dose date + 1*). In the case that a patient has not decreased in the WHO scale at time of analysis or withdraws from the study before leaving the hospital, they will

be censored at their date of last assessment in the data cut or early discontinuation date, respectively.

Time to improvement will be analyzed using the Kaplan-Meier methods as described in the above time to event analyses.

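### In-hospital deaths are called failures but censored in time to discharge, time to improvement has no rule for death, and one date rule can censor a known death in overall survival

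*SAP*

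**What the plan says.** All references are to SAP version 2.0.

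- **Time to hospital discharge (4.9.3).** "Patients who die before leaving the hospital will be considered failures (did not achieve hospital discharge". The sentence goes on to assign these patients a time running from first dose to death and to censor them there. The method follows: "The time to hospital discharge survival will be analyzed using Kaplan-Meier methods". Cox models are optional. No competing-risk method is named.
- **Time to improvement (4.9.3).** The censoring rule begins "In the case that a patient has not decreased in the WHO scale at time of analysis", adds patients who withdraw, and has them "be censored at their date of last assessment in the data cut or early discontinuation date, respectively". Death is not mentioned.
- **Partial death dates (4.9.1.3).** "b) If the day is missing, then assign '01" gives the 1st of the month. If this makes the overall survival time negative, "the patient will be censored for overall survival at the randomization date".
- **Overall survival (4.9.3, Mortality at Day 28).** Time to death is date of death minus first dose date plus one. The regular censoring rule covers only patients with no recorded death.

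Section 3.3.1 lists time to improvement as key secondary, and time to discharge and Day 28 mortality as additional secondary.

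**The concern.** Kaplan-Meier treats a censored patient as someone who could still have the event later, at the same rate as those still at risk. A patient who has died in hospital cannot be discharged. The discharge rule therefore does not deliver the failure status that its own sentence announces: deaths leave the risk set, and the estimated curve answers how many would be discharged if nobody died.

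For improvement, death is level 7 on the WHO scale (4.9.2). A patient who dies without improving is thus simply someone whose score has not decreased, and is censored like any other.

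In overall survival the problem is more direct. Under one date condition, a patient known to have died contributes no death and no follow-up. This conflicts with the regular rule, which reserves censoring for patients without a recorded death. It also uses the randomisation date in an analysis whose clock starts at first dose.

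At stake are the discharge and improvement percentages read from the curves, and possibly some events in the survival curve and hazard ratio.

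**Working it through.** The SAP states no discharge or mortality rate, so there is no figure of its own to reproduce. The sizes below rest on assumed rates.

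**1. Discharge by Day 28**

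Assume constant daily hazards: λ for discharge and μ for death in hospital.

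- Deaths censored at death: 1 − KM(28) = 1 − exp(−28λ). This does not contain μ.
- Death as a competing event: CIF(28) = λ/(λ+μ) × [1 − exp(−28(λ+μ))].

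Set λ so that 1 − KM = 90%: λ = −ln(0.10)/28 = 0.0822 per day. Solve μ for each assumed Day 28 mortality.

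| Day 28 mortality | μ per day | 1 − KM | CIF | Overstatement (points) |
|---|---|---|---|---|
| 2% | 0.0019 | 90.0% | 88.5% | 1.5 |
| 5% | 0.0048 | 90.0% | 86.2% | 3.8 |
| 10% | 0.0100 | 90.0% | 82.4% | 7.6 |
| 20% | 0.0220 | 90.0% | 74.6% | 15.4 |

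A second set of assumptions gives the same picture. With λ = 0.09 and μ = 0.006, 0.012 and 0.020, Day 28 mortality is 5.8%, 11.1% and 17.3%. The true proportion discharged is 87.4%, 83.2% and 78.1%, while 1 − KM is 92.0% in all three.

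**2. Improvement**

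No separate calculation is needed. The same formula applies with an improvement hazard in place of λ; only the censoring date differs (last assessment or early discontinuation, not death).

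**3. When the overall survival rule censors a known death**

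Imputed time = 1st of the death month − first dose date + 1.

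- Death in the same month as a first dose on day d: time = 1 − d + 1 = 2 − d, which is negative only for d ≥ 3.
- Death in a later month: the imputed date falls after first dose, so the time is positive and the death stays an event.

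| First dose | Death | True time | Imputed time | Result |
|---|---|---|---|---|
| 12 Oct | 20 Oct | 9 | −10 | censored at randomisation |
| 12 Oct | 5 Nov | 25 | 21 | event |
| 2 Oct | 20 Oct | 19 | 0 | event |
| 1 Oct | 20 Oct | 20 | 1 | event |

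**4. How often, among deaths with a missing day**

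Take first-dose dates spread evenly over two calendar years. With death days uniform over Days 1–28, 1–14 and 1–10, the share censored is 49%, 72% and 79%. Alternatively, take first dose uniform over days 1–30 of a month and exponential time to death with mean 7, 10 and 14 days: the share is 72%, 64% and 54%.

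**The case against.** **Censoring at death is a recognised analysis.** It estimates a cause-specific hazard, and a Cox model fitted that way has a clear meaning. This stands. The defect lies in reading 1 − KM as the proportion discharged, and in announcing deaths as failures while censoring them. It is shown above as an error within an arm: with similar mortality both arms shift alike, and no between-arm bias has been computed.

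**The size may be small.** Patients may enter at WHO level 3, without oxygen. At 2% mortality the discharge error is about 1.5 points. This stands, and the range starts there.

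**A reader might infer that every death with a missing day is censored in overall survival.** The SAP does not say so. The default keeps the death as an event on the 1st of the month; censoring needs a negative time. Such dates may also be rare: the WHO scale is scored daily in hospital, so partial dates are likelier for deaths after discharge that are learned of by telephone. The number affected may be zero.

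**A reader might infer that improvement is censored at death by a stated rule.** There is no such rule. The handling follows from silence, and the date is last assessment or early discontinuation.

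**A reader might infer that the plan conceals harm.** It does not support that. Day 28 mortality is a count of deaths with a CMH test and none of this censoring. Death, as level 7, also counts in the primary endpoint and in time to progression, and deaths appear in the adverse event tables and listings.

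**Conclusion.** Two stated rules give wrong results if followed exactly, and one gap has a similar effect.

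- **Discharge:** wrong as written. The SAP contradicts itself within one sentence, and 1 − KM overstates the proportion discharged by about 1.5 to 15 points for Day 28 mortality of 2% to 20%. This assumes constant hazards and 90% on the Kaplan-Meier scale; none of these rates comes from the SAP.
- **Improvement:** an omission on a key secondary endpoint, with the same direction of error.
- **Overall survival:** a known death is censored at randomisation when its day is missing, it falls in the month of first dose, and first dose was on day 3 or later. This conflicts with the regular censoring rule. It would reach roughly half to three quarters of deaths with a missing day (49% to 79% across the death timings assumed), but the number of such deaths is unknown and may be small.

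The consequences are confined to these time-to-event analyses. The primary result and binary Day 28 mortality do not change.

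**What to change.** - **Discharge and improvement:** treat death without the event as a competing event, and report cumulative incidence with Gray's test or a Fine-Gray model. Alternatively, keep these patients in the risk set as non-events by censoring them at Day 28. Write the chosen rule under both endpoints, so that improvement no longer depends on silence.
- **Missing day of death:** impute the latest of the 1st of the month, the first dose (or randomisation) date and the date last known alive. Always count the death as an event, and delete the clause that censors at randomisation.

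The cost is a few sentences of SAP text and standard code; no new data are needed. The downside is that discharge and improvement percentages become slightly less favourable.

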#### Time to Improvement

Time to improvement is the time in which the patient sees a decrease after first study treatment in the WHO 7-point ordinal scale from baseline to a value at least one level lower in days (*date of decrease in WHO scale - first dose date + 1*). In the case that a patient has not decreased in the WHO scale at time of analysis or withdraws from the study before leaving the hospital, they will

be censored at their date of last assessment in the data cut or early discontinuation date, respectively.

Time to improvement will be analyzed using the Kaplan-Meier methods as described in the above time to event analyses.

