## 2 STUDY OBJECTIVES

### 2.1 Primary Objective

- To evaluate efficacy of RESP301 in preventing progression of hospitalized COVID-19 participants at level 3 or 4 in the modified World Health Organization (WHO) ordinal scale into higher levels.

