### 3 INVESTIGATIONAL PLAN

### 3.1 Overall Study Design and Plan

This is an open-label, randomized, multicenter, parallel group, concurrent, controlled study using a sequential adaptive design to evaluate the efficacy and safety of RESP301 added to standard of care (SOC) in hospitalized patients with COVID-19 (WHO ordinal scale grade 3 & 4).

Central stratified randomization of 300 subjects to assign participants into one of the study treatment arms will occur as follows, RESP301+SOC or SOC (control), with a randomization ratio of 2:1 using an interactive voice response system (IVRS)/interactive web response system (IWRS). Participants will be stratified by country and presence of risk factors for severe outcomes of COVID-19, based on comorbidities and age as follows:

1. Age  $>65$  years
2. Ongoing or currently treated diabetes mellitus
3. Ongoing or currently treated hypertension
4. Ongoing or currently treated cardiovascular disease
5. Ongoing or currently treated chronic lung disease
6. Cancer history of less than 3 years, basal cell skin carcinoma excluded
7. Ongoing or currently treated chronic kidney disease

Participants will be stratified as no risk factor (none of the above criteria), one risk factor (one single of the above) or high-risk factor (2 or more of the above).

There are 3 phases in the overall study design: Screening Period, Intervention Period, Follow-up Period. Figure 1 displays the study schematic.

**Screening Period**– Patients will be screened up to 2 days prior to treatment administration. Upon signing informed consent, the patient enters the screening phase and is assessed for the inclusion/exclusion criteria. If all eligibility criteria are met, the patient moves into the intervention period.

[figure not shown]
**Intervention Period** – The intervention period starts on Treatment Initiation (Day 1). Patients will receive treatment three times a day up to Day 10. Patients may end treatment earlier than Day 10 if their symptoms subside following the criteria outline in the protocol section 4.1.

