**Figure 2: The National Early Warning Score 2 (NEWS 2) scoring system**

Physiological parameter	Score						
	3	2	1	0	1	2	3
Respiration rate (per minute)	≤8		9–11	12–20		21–24	≥25
SpO 2 Scale 1 (%)	≤91	92–93	94–95	≥96			
SpO 2 Scale 2 (%)	≤83	84–85	86–87	88–92 ≥93 on air	93–94 on oxygen	95–96 on oxygen	≥97 on oxygen
Air or oxygen?		Oxygen		Air			
Systolic blood pressure (mmHg)	≤90	91–100	101–110	111–219			≥220
Pulse (per minute)	≤40		41–50	51–90	91–110	111–130	≥131
Consciousness				Alert			CVPU
Temperature (°C)	≤35.0		35.1–36.0	36.1–38.0	38.1–39.0	≥39.1	

### Mortality at Day 28

Incidence of mortality by Day 28 is the number of patients who have died by Day 28 and the percentage of patients reaching this endpoint will be summarized by treatment group. A CMH test will be used to test for a treatment effect of RESP301 + SOC versus SOC Alone after adjusting for baseline clinical status. Odds ratios of the treatment effect (RESP301 + SOC versus SOC Alone) with corresponding 95% confidence intervals (CI) will be estimated using a logistic regression model with baseline clinical status as a covariate. A treatment by baseline clinical status interaction may be added to the model along with other covariates of interest.

Overall survival will also be analyzed using time to event methods. Time to death is defined as the time from treatment start to death in days (*date of death – first dose date + 1*). Patients without a recorded death will be censored at their completion or at their early discontinuation date if they withdrew early or at their date of last assessment if they are alive and ongoing in study at time of analysis (*completion date/early discontinuation date/last assessment date – first dose date +1*). Reasons for censoring will be summarized.

The total number of patients with an event, the total number censored and Kaplan-Meier survival estimates with associated 95% CI (25th percentile, median, and 75% percentile, proportion surviving at Days 7, 10, 14, and 28) will be presented by treatment group. A survival plot will be produced with the probability of an event (0 to 100%) along the Y-axis and time in days along the X-axis.

The number of patients at risk will be presented along the X-axis. The hazard ratio of RESP301 + SOC versus SOC Alone with corresponding 95% CI and p-values will be estimated from a Cox Proportional model adjusting for treatment, and patients randomized strata.

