#### Time to Progression

Time to improvement is the time in which the patient sees an increase after first study treatment in the WHO 7-point ordinal scale from baseline to a value at least one level higher in days (*date of increase in WHO scale - first dose date + 1*). In the case that a patient has not increased in the WHO scale at time of analysis or withdraws from the study before leaving the hospital, they will be censored at their date of last assessment in the data cut or early discontinuation date, respectively.

Time to progression will be analyzed using the Kaplan-Meier methods as described in the above time to event analyses.

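### Time to improvement and time to progression now mix level-3 and level-4 entrants, but no binding adjustment of the treatment comparison for baseline WHO level is stated

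*SAP*

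**What the plan says.** The primary objective (SAP 2.1, version 2.0) concerns "hospitalized COVID-19 participants at level 3 or 4 in the modified World Health Organization (WHO) ordinal scale". Section 3.3.1 lists time to improvement and time to progression as key secondary endpoints, each defined as a change of at least one level. In version 1.0 all patients entered at level 4 and the events were fixed levels: below 4 for improvement, above 4 for progression.

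The analysis wording in 4.9.3 did not change with the definitions. For improvement: "Time to improvement will be analyzed using the Kaplan-Meier methods as described in the above time to event analyses". For progression: "Time to progression will be analyzed using the Kaplan-Meier methods as described in the above time to event analyses".

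Two analyses stand above those sentences:
- **Overall survival** (under Mortality at Day 28): the hazard ratio is "estimated from a Cox Proportional model adjusting for treatment, and patients randomized strata".
- **Time to hospital discharge**: "If data allows, survival estimates will be stratified by baseline clinical status". A Cox model with the randomisation strata is optional there.

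The randomisation strata (3.1, 4.9.1.2) are country and risk-factor group. Baseline WHO level is not among them, nor in the subgroup list (4.9.1.6). It is collected and summarised at baseline (4.6).

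**The concern.** The event definitions were adapted to the wider population and the analysis was not. A single curve or hazard ratio now combines patients whose first qualifying step differs, and randomisation does not balance the factor that decides which step applies.

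The SAP treats baseline clinical status as worth adjusting for in other places: the general repeated-measures and CMH statements in 4.2, and the CMH test and logistic model for Day 28 mortality in 4.9.3. It does not do so firmly for the two endpoints defined relative to baseline level. I take baseline clinical status to mean baseline WHO level; the SAP does not define the term.

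At stake are the precision and readability of two key secondary results. The primary test is not affected.

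**Working it through.** The available text gives no event rate, hazard ratio or power for either endpoint (the sample-size sections are redacted), so there is no plan figure to reproduce.

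**Step 1. Smallest qualifying event, from the scale in 4.9.2**

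| Entry level | Improvement | Progression |
|---|---|---|
| 3 | leaving hospital (level 2 or 1) | starting supplemental oxygen, or worse |
| 4 | coming off oxygen, or better (discharge included) | high-flow oxygen or non-invasive ventilation, or worse |

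**Step 2. Chance imbalance in entry level**

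Inputs from 3.1: "Central stratified randomization of 300 subjects" and "with a randomization ratio of 2:1", hence 200 and 100. The level-3 share s is not given; I assume 30% to 50%.

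SD of the between-arm difference = √[s(1 − s)(1/200 + 1/100)]
- s = 0.5: √(0.25 × 0.015) = 0.0612
- s = 0.3: √(0.21 × 0.015) = 0.0561

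The chance of a difference above 10 points is 10.2% (s = 0.5) or 7.5% (s = 0.3). For a difference above 5 points it is 41% or 37%.

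**Step 3. Effect on the hazard ratio**

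Simulation: 2,000 trials per scenario, N = 300 at 2:1, exponential times, censoring at Day 28. A Cox model ignoring level was compared with one stratified by level. None of these rates is in the SAP:
- level-3 share 30% or 50%
- level-3 to level-4 hazard ratio 1/3, 1/2, 2 or 3
- level-4 control hazard for improvement 0.10 per day (median ln 2/0.10 = 6.9 days)
- level-4 control hazard for progression 0.0127 per day (1 − exp(−0.0127 × 28) = 30% by Day 28)

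| Range over scenarios | Improvement, within-level HR 1.40 | Progression, within-level HR 0.50 |
|---|---|---|
| HR, level ignored | 1.32–1.38 | 0.50–0.52 |
| HR, stratified by level | 1.39–1.41 | 0.50 |
| Power, level ignored | 55–73% | 60–90% |
| Power, stratified | 70–77% | 62–93% |
| Power gain within a scenario | 4–18 points | 0.3–3.4 points |

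With no treatment effect, the two-sided rejection rate of the comparison that ignores level was 3.8% to 5.4% (Monte Carlo error about 1 point), which is nominal.

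Across both endpoints, a 10-point imbalance in level-3 share multiplied the hazard ratio by 0.89 to 1.13 when level was ignored, and by 0.99 to 1.02 when the model was stratified.

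**Step 4. Dependence on the gap between levels**

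Large-sample fits for improvement, half the patients at each level:
- Balanced arms, within-level HR 1.50: read as 1.39 (medians 4 and 12 days), 1.45 (5 and 10 days) or 1.48 (6 and 8 days).
- No treatment effect, 12-point imbalance (the edge of the 95% range): 1.08 to 1.09 (medians 5 and 10) or 1.04 (6 and 8).
- No treatment effect, one-standard-error imbalance of 6 points, medians 5 and 10: 1.04.

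**The case against.** The other side has several fair points.

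- **Different rates are not guaranteed.** A reader might infer that the two entry groups must have different hazards because their thresholds differ. The SAP does not support that. The events overlap, since a level-4 entrant discharged directly also improves and a level-3 entrant who is ventilated or dies also progresses. A less ill patient with a larger first step may improve at much the same rate as a sicker patient with a smaller one. This stands, and every effect size above is conditional on assumed rates.
- **No false-positive problem.** A reader might infer an invalid test. Over repeated randomisations the error rate is nominal. Chance imbalance affects any unstratified prognostic factor. This stands.
- **The smaller hazard ratio is a different quantity.** With balanced arms, the unadjusted value estimates a marginal effect and is not a wrong estimate of it. This stands, but the lost power is real.
- **Part of the remedy may already be planned.** The cross-reference is plural, so the conditional stratification under time to discharge may carry over. It may, but the text does not say so. Even then it covers survival estimates, only if the data allow, and leaves the hazard ratio unadjusted.
- **A Cox model may not be intended.** The sentences name Kaplan-Meier methods only, and the nearest Cox statement is optional. That is a further reason to state the method.
- **The consequence is limited.** The multiplicity section sets no testing sequence for secondary endpoints. In addition, the SAP's own use of baseline status is uneven: the respiratory-outcomes model in 4.9.3 uses risk group where 4.2 names clinical status.

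**Conclusion.** The point holds as a gap in specification. Two key secondary endpoints are defined relative to baseline level, pool two entry levels, and carry no binding adjustment of the treatment comparison for that level.

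The consequence is reduced protection against chance imbalance, plus attenuation and lost power if event rates differ by level. Under the assumed rates this is material for improvement and slight for progression, so a claim that both endpoints are appreciably diluted would go too far. With similar rates at the two levels the loss is small for both.

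The imbalance figure rests only on the 300 patients, the 2:1 ratio and an assumed level-3 share. The hazard-ratio and power figures also rest on assumed event rates and treatment effects. The change is worth making as a free improvement, not as the repair of an invalid analysis.

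**What to change.** In 4.9.3, under both Time to Improvement and Time to Progression, replace the cross-reference with an explicit statement:

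- The treatment hazard ratio and its 95% CI come from a Cox model stratified by baseline WHO level (3 versus 4), with country and risk group as randomised as covariates.
- Any log-rank test is also stratified by baseline WHO level.
- Kaplan-Meier curves are shown by arm within each baseline level.

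This also settles whether a Cox model is planned and whether the conditional sentence under time to discharge applies. The cost is a few lines of SAP text, one stratification term and an extra set of curves, using a baseline value already collected. It should be fixed before database lock.
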